### 5.3 REASONS NOT TO IMPLANT A STUDY IOL

At the time of cataract surgery, but prior to IOL implantation there are operative adverse events that may prevent implantation of the designated IOLs for this clinical study. These criteria include, but are not limited to:

- 1) Intraoperative complications during the phacoemulsification and IOL implant that require any other additional procedures or further intervention
- 2) Significant detachment of Descemet's membrane
- 3) Significant corneal endothelial damage
- 4) Wound burn
- 5) Capsular tear, iris incarceration or damage, posterior capsular rupture, vitreous loss or prolapse, or zonular weakness, dehiscence or rupture
- 6) Significant anterior chamber bleeding
- 7) Excessive iris mobility or need for iris manipulation
- 8) Mechanical or surgical manipulation required to enlarge the pupil prior to or at IOL implantation
- 9) Other ocular conditions or complications that could compromise IOL stability
- 10) Bag sulcus, sulcus-sulcus or unknown placement of haptics
- 11) Any method of anterior capsulotomy other than circular continuous capsulorhexis (e.g., anterior capsular tears or any areas of 'can-opener' capsulotomy or FLACS)
- 12) Capsular fibrosis or other opacity
- 13) Optic and/or haptic damage/amputation
- 14) Inability to fixate IOL in desired position

If an operative adverse event prevents implantation of the investigational IOL in the first eye and the IOL did not touch the eye, the subject should be implanted with a non-study IOL instead and discontinued from the study, followed under the Investigator's normal standard of care.

If an operative adverse event prevents implantation of the investigational IOL in the first eye and the IOL touched the eye, the Investigator should follow the subject through resolution of any adverse events (AEs) and then discontinue the subject. If an operative AE prevents implantation of the investigational IOL in the second operative eye, the Investigator should follow the subject through resolution of any AEs for the second operative eye and the subject should remain in the study and attend all study visits for the first operative eye.

### 5.4 SCREEN FAILURES

An enrolled subject who fails to meet eligibility criteria and/or discontinues from the study before the first eye is implanted will be considered a screen failure and exited from the study.

## 5.5 STRATEGIES FOR RECRUITMENT AND RETENTION

Study participants will be recruited from the investigator's patient population, referrals, or other outreach methods. Written recruitment materials directed to potential study participants must be approved by the overseeing IRB.

Where possible, candidate participants may be pre-screened via review of their medical charts to evaluate potential eligibility based on study inclusion/exclusion criteria. During the informed consent discussion, the potential participant's willingness and ability to meet the follow-up requirements will be evaluated. Those who elect to sign the study informed consent form (ICF) will be considered enrolled in the study and given a study identification code. At/after the time of enrollment, the subject will be evaluated at the Preoperative Visit for study eligibility based on inclusion/exclusion requirements.

Study site personnel should take the following steps to minimize the likelihood of early termination during the study:

- During the Preoperative Visit, emphasize the importance of returning for all study follow-up visits and thoroughly evaluate the study subject for potential health or motivational issues or other life circumstances that may negatively affect compliance with the study follow-up visit schedule.
- Evaluate research staff flexibility to work around personal difficulties encountered by the subject related to protocol compliance (e.g., appointment times).
- Attempt to schedule subject follow-up visits early in the visit window to facilitate rescheduling within the window, if necessary.
- Attempt to follow-up on subjects who do not return for scheduled examinations.

## 6 STUDY INTERVENTION

### 6.1 STUDY DEVICES

#### 6.1.1 INVESTIGATIONAL DEVICE DESCRIPTION

The FINEVISION HP Trifocal IOL, shown in Figure 1, is a diffractive IOL designed to provide recipients with intermediate, near and distance vision. These lenses provide three focal points by combining two superimposed diffractive profiles, one with a +1.75 D addition at the IOL plane for intermediate vision, and the other with a +3.50 D addition for near vision. The light-energy distribution sends the greatest amount of light to distance, then near, and the least to intermediate.

Figure 1: FINEVISION HP Trifocal IOL

The FINEVISION HP Trifocal IOL is available in powers from +10.0 D to +30.0 D in 0.50 D steps. The single-piece IOL has a double-C-loop haptic design and 5° vault. The 4 haptics are of 0.34 mm thickness. The optic portion diameter is 6.0 mm and the IOL total diameter is 11.4 mm. The device has a square edge of 360° aiming at optimal lens-tissue contact. The IOL has a biconvex aspheric optic (-0.11 microns of spherical aberration at 5 mm pupil) to adjust for the positive spherical aberration of the cornea. [REDACTED]

The IOL is made with the proprietary medical quality hydrophobic acrylic (GFY) (meth) acrylic material. The material includes an UV blocker and a blue light filtering chromophore.

[REDACTED]

#### 6.1.2 CONTROL DEVICE DESCRIPTION

AcrySof SN60AT [REDACTED] Monofocal IOL Model SN60AT [REDACTED] from Alcon (Fort Worth, TX) is a hydrophobic, ultraviolet filtering, foldable monofocal IOL with biconvex single-piece design comprised of a central optic and 2 open-loop haptics. The optic is 6.0 mm in diameter and the lens has a total diameter of 13.0mm. The lenses will be available in powers +10.0 D to +30.0 D in 0.50 D increments.

[REDACTED]

T [REDACTED]

## 6.2 DEVICE ACCOUNTABILITY AND STORAGE

### 6.2.1 ACQUISITION AND ACCOUNTABILITY

Throughout the clinical study, the Investigator will be responsible for the accounting of all test and control IOLs and will ensure that the investigational products are used in accordance with the manufacturer's manual of procedures (MOP) and directions for use (DFU).

Upon receipt of the investigational product (IP), shipment records will be verified by comparing the Shipping Receipt Confirmation to the devices actually received at the site. If a discrepancy is noted, the Sponsor or designee must be notified immediately. Accurate records of receipt and disposition (dispensing log) of the study devices (e.g., dates, subject number, etc.) must be maintained by the Investigator or authorized site representative.

Throughout the study, the Investigator must maintain records of IP dispensed and implanted for each subject. All IP sent to the Investigator must be accounted for and in no case be used in an unauthorized manner.

The Investigator is responsible for proper disposition of all unused IP at the conclusion of the study, according to the instructions provided by the Sponsor.

### 6.2.2 PACKAGING AND LABELING

The FINEVISION HP investigational lenses will be provided sterile in blisters and labeled with the lens ID, lot number, expiry date. Each IOL will bear a sticker with the following statement: 'CAUTION--Investigational device. Limited by Federal (or United States) law to investigational use.'

The AcrySof SN60AT [REDACTED] Monofocal IOL Model SN60AT [REDACTED] control lenses will be provided sterile in blisters and labeled with the lot number and expiry date along with the standard manufacturer's packaging instructions.

To maintain product sterility and integrity, the study devices will be supplied in their original packaging and used according to the appropriate device instructions.

### 6.2.3 PRODUCT STORAGE AND STABILITY

Study devices should be stored in a secure area according to the package labels.

## 6.3 MEASURES TO MINIMIZE BIAS: RANDOMIZATION AND MASKING

Subjects will be randomly assigned to receive either the investigational FINEVISION HP IOL or the AcrySof monofocal IOL in both eyes according to the randomization schedule (2:1 ratio) provided. Randomization will be stratified by site. The randomization schedule will be created using computer-generated randomization methodology by an independent statistician who is not involved in the day-to-

day conduct of the study. Randomization is to occur following the completion of informed consent and screening procedures.

In order to minimize bias, site personnel performing postoperative study assessments of visual performance, including manifest refraction, visual acuity, defocus curve testing and contrast sensitivity will be masked to subject treatment assignment until after the final database lock (“masked assessors”). Any unmasking of the masked assessor or any study subjects must be reported to the Sponsor. Every attempt should be made to have the same masked assessor perform the same postoperative measurements for an individual subject throughout the subject’s study participation.

Subjects will also be masked to their assigned treatment group (test or control group). Any material that may indicate the subjects’ assigned treatment, e.g., packaging, documents, etc., should be removed from areas where subjects and/or masked personnel may see it. Unmasked personnel should further be instructed to avoid conversation and communication with masked personnel, subjects and persons other than the study investigator regarding subjects’ assignments, outcomes, clinical courses and all other information potentially relevant to the study and its conduct.

## 7 PARTICIPANT DISCONTINUATION/ WITHDRAWAL

### 7.1 PARTICIPANT DISCONTINUATION/ WITHDRAWAL FROM THE STUDY

Discontinued subjects are those who withdraw from the study after the study informed consent document is signed and before the final visit is completed. Subjects who sign the study consent document but fail to meet eligibility criteria or withdraw prior to study IOL implantation in the first eye shall be considered discontinued due to screen failure.

A subject may be discontinued prior to the final study visit for any of the following reasons, including but not limited to:

- Screen failure
- Adverse event(s); note that subjects should be followed within the study until adverse event resolution or stability
- Investigator’s request (e.g. medical decision)
- Voluntary withdrawal (subject’s request)
- Death
- Study terminated by Sponsor
- Loss to follow-up

Prior to discontinuing a subject, every effort should be made to contact the subject to schedule a final study visit and obtain as much follow-up data as possible. Discontinued subjects should thereafter be followed outside of the study protocol according to the Investigator’s normal standard of care.

The reason for participant discontinuation or withdrawal from the study will be recorded on the Exit Case Report Form (CRF).

Randomized subjects who do not receive a study IOL may be replaced. Randomized subjects who receive a study IOL and are discontinued or withdraw from the study afterwards will not be replaced.

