## 8 STUDY ASSESSMENTS AND PROCEDURES

Study participants will be evaluated at a Preoperative Visit. For subjects who qualify for further study participation, the primary eye will be determined, the subject will be randomized to receive the assigned study IOL, and surgery will be scheduled to occur between 1 and 90 days after the Preoperative visit.

Cataract surgery/IOL implantation will be performed for the primary eye and the subject will be scheduled to return for follow-up visits and examinations at the Day 1, Week 1, Month 1, Month 6, and Month 12 time periods, consistent with study visits described in ISO 11979-7 (Form 0 through Form 5). Cataract surgery/IOL implantation in the second operative eye will be scheduled 7 – 30 days after primary eye surgery in a manner such that follow-up examinations for the second operative eye may be performed when the subject returns for scheduled primary eye visits. Data collected from each visit, including any abnormal findings, will be documented in the source records and recorded on study eCRFs.

The timing and frequency of assessments/procedures to be performed at each visit is outlined in the SoA.

Methodology for study examinations is presented in the Manual of Procedures.

### 8.1 PREOPERATIVE VISIT (DAY -90 TO DAY -1): VISIT 0

The Preoperative Visit must occur no more than 90 days and no less than 1 day prior to the Operative Visit. Informed consent must be obtained prior to performing study-specific procedures not part of the

investigator's routine standard of care. Subjects who sign the ICF will be given a unique 4-digit screening number, where the first two digits corresponds to the site number.

At this visit, the following activities will be performed:

- Ocular and significant non-ocular medical history\*
- Projected Visual Acuity\*
- UCDVA\*
- BCDVA\*
- Target Refraction/IOL power calculation/Axial Length/Anterior Chamber Depth (biometry)\*
- Keratometry\*
- Corneal Topography\*
- Manifest Refraction (ETDRS)\*
- Photopic/mesopic pupil size\*
- Intraocular Pressure\*
- Slit Lamp Exam\*
- Dilated Fundus Exam\*

*\* These assessments, if performed during routine standard of care exams up to 90 days before the subject Preoperative Visit, may be used as qualifying preoperative assessments prior to consent. All study specific evaluations not included in a routine cataract evaluation must be performed in the preoperative time period (Day -90 to Day -1).*

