## 8.2 OPERATIVE VISIT (DAY 0): VISIT 00 A/B

The Operative Visit for the first operative eye must occur on Day 0. The Operative Visit for the second operative eye must be scheduled between Days 7 – 30, inclusive.

At the Operative Visit, prior to surgery, subjects will be assessed to reconfirm eligibility and any changes in concomitant medications or medical/ocular conditions will be recorded on the appropriate CRF. If the subject is determined no longer to be eligible, he/she will be discontinued from the study prior to cataract surgery and considered a screen failure.

If operative complications prevent implantation of the investigational IOL (see Section 5.3 – Reasons Not to Implant a Study IOL), a non-study IOL may be implanted instead. Subjects who were not exposed to the study IOL will be exited from the study and followed per the investigator's standard of care.

No additional refractive procedures are to be performed during the operative procedure or throughout the postoperative study period.

The Investigator should refer to the Manual of Procedures for more detailed guidance on FINEVISION HP implantation and AcrySof SN60AT [REDACTED] implantation. Subjects must be targeted as closely as possible for emmetropia. Surgeons may use their personalized A-constant for model SN60AT [REDACTED].

For study visits designated A or B, 'A' represents the first eye implanted (Eye A), and 'B' represents the second eye implanted (Eye B). Monocular assessments will be performed at **Visits 00 A/B, 1 A/B, 2 A/B, and 3 A/B** for only **Eye A** or only **Eye B**, respectively, unless binocular assessments are specified (See Schedule of Activities, Section 1.3). At Visits 4 and 5, monocular assessments and binocular assessments will be completed for both eyes.

### 8.3 POSTOPERATIVE VISITS: VISIT 1 THRU VISIT 5

Postoperative visits should be scheduled according to the following visit window schedule:

- Visit 1 A: 1-2 days after surgery on the first eye
- Visit 1 B: 1-2 days after surgery on the second eye
- Visit 2 A: 7-14 days after surgery on the first eye
- Visit 2 B: 7-14 days after surgery on the second eye
- Visit 3 A: 30-60 days after surgery on the first eye
- Visit 3 B: 30-60 days after surgery on the second eye
- Visit 4: 150-180 days after surgery on the first eye
- Visit 5: 360-420 days after surgery on the first eye

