### Primary Strategy

1. Withdrawal due to physician decision: missing data assumed to be MNAR. Control-based multiple imputations will be completed for superiority hypotheses and treatment-based multiple imputations will be completed for non-inferiority hypotheses. [hypothetical strategy]
2. Missing data without withdrawal or withdrawal due to reasons other than due to physician decision: missing data assumed to be MAR. Treatment-based multiple imputations will be completed. [hypothetical strategy]

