## 9. Disposition of Subjects

The total number of screened subjects and screen failures prior to randomization will be presented. The number of subjects randomized as well as the number and percentage of subjects with at least one eye implanted with an IOL and subjects not implanted with an IOL will be presented by treatment group and overall. Inclusion in the ITT Set, All-Implanted Analysis Set, Best Case Set, Safety Set, [REDACTED]

[REDACTED] as well as study completion status will be summarized by treatment group and for all subjects using discrete summary statistics. The number of discontinuations and reasons for discontinuation will be summarized by treatment group and for all subjects using discrete summary statistics. A subject listing will be provided which includes the study exit date, study completion status, and the reason for premature study discontinuation (if applicable).

In addition, the prevalence of any protocol deviations, major protocol deviations, and minor protocol deviations will be summarized by treatment group and for all subjects using discrete summary statistics. A subject listing will be provided for protocol deviations which will include the date of the deviation, the visit at which the deviation occurred, the deviation code, the deviation description, action taken in response to the protocol deviation, and the classification of whether the deviation was judged to be major or minor in a masked review.

Subject accountability at each of the post-operative visits will be summarized overall for all subjects and by treatment group for first operative eyes and second operative eyes using discrete summary statistics, based on Table A.1 from ISO 11979-7.

Details of the study randomization, including the first eye to be implanted, randomization number, randomization date, randomized treatment, and actual treatment, will also be included within a subject listing.

A subject listing indicating whether a subject met all eligibility criteria, was a screen failure, the screen failure date (if applicable), and the eligibility criteria not met (if applicable) will also be provided.

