### 13.1.2 SENSITIVITY ANALYSIS II

The primary analyses will be repeated for the ITT Set using the primary multiple imputation strategy as specified in [Section 13.1](#) for both primary effectiveness endpoints.

For subjects from the ITT Set who are not implanted with an IOL, the first operative eye will be imputed using the same criteria for selecting the first operative eye as described in [Section 8.1](#).

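### 'Screen failure' is applied to subjects already randomised, which merges their reasons for leaving and can misroute imputation in the ITT check of DCNVA and DCIVA

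*Protocol*

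**What the plan says.** **Timing.** Protocol 6.3: "Randomization is to occur following the completion of informed consent and screening procedures". The schedule of activities places randomisation at Visit 0, and Protocol 8 adds that "surgery will be scheduled to occur between 1 and 90 days after the Preoperative visit". Eligibility is reviewed again at the operative visit.

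**Label.** Three protocol sections apply it to anyone who leaves before the first eye is implanted, with no exception for randomised subjects:
- 5.4: a subject who "discontinues from the study before the first eye is implanted will be considered a screen failure and exited from the study".
- 7.1: those who "withdraw prior to study IOL implantation in the first eye shall be considered discontinued due to screen failure".
- 8.2, on the day of surgery, for a subject found no longer eligible: "he/she will be discontinued from the study prior to cataract surgery and considered a screen failure".

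**Contrary use.** Protocol 9.2 takes the 7% screen-failure loss between enrolment (539) and randomisation (501). SAP 9 says: "The total number of screened subjects and screen failures prior to randomization will be presented".

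**Imputation.** Under SAP 8.2, withdrawal by physician decision is MNAR, with control-based imputation for superiority hypotheses. For everything else: "Missing data without withdrawal or withdrawal due to reasons other than due to physician decision: missing data assumed to be MAR", imputed from the subject's own arm. The sample code in SAP 13.1 makes this split on the coded discontinuation reason alone. SAP 13.1.2 carries it into the ITT set: "The primary analyses will be repeated for the ITT Set using the primary multiple imputation strategy". SAP 13.2 repeats the DCNVA sensitivity analyses for DCIVA.

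**The concern.** The primary effectiveness set contains only successfully implanted eyes with a postoperative visit, so a randomised subject who is never implanted leaves the primary analysis. Protocol 6.3 masks subjects and visual-performance assessors. It does not list the surgeon, and the assignment is known before surgery is scheduled (8.1). Exclusion between randomisation and implantation could therefore depend on the arm. The main checks on that are the disposition tables and the ITT sensitivity analysis, and both use the recorded reason for leaving.

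A label that covers several different reasons weakens both checks. The table cannot separate a surgeon's decision from a subject's change of mind. The imputation rule written for physician decisions may also not be triggered in the cases it was meant for. For a superiority comparison, own-arm imputation of a test-arm subject is the favourable direction.

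**Working it through.** **1. Planning figures reproduce.** Enrolment: 501 / (1 - 0.07) = 538.7, so 539, which confirms that 9.2 counts screen failures before randomisation. Allocation: 501 x 2/3 = 334 test and 167 control. For DCNVA and DCIVA, SE = 0.14 x sqrt(1/300 + 1/150) = 0.014 against a planned difference of -0.10 logMAR. Power is above 99.99%, consistent with the stated figure of more than 99%.

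**2. Path of one subject.** Take a test-arm subject whom the investigator withdraws after randomisation and before surgery.
- Under 5.4 and 7.1 the exit is a screen failure.
- SAP 9 counts the subject among those randomised and not implanted, by arm. The reasons table shows the coded reason.
- The ITT set keeps the subject. The coded reason is not physician decision, so the MAR rule applies and DCNVA is imputed from the test arm.
- With the true reason recorded, the control-based rule would apply.

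**3. BCDVA.** Under the primary strategy both rules are treatment-based for non-inferiority, so the shift is 0.

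**4. Size for DCNVA.** The documents give no count of such subjects, so k is an assumption. Take k of them in addition to 334 implanted test subjects (7.1 allows replacement), a control mean of 0 and a test mean of -0.10. The extreme bound is k = 539 - 501 = 38: every planned screen failure occurs after randomisation, in the test arm, by physician decision.

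*Upper figure: rerouted subjects take the control mean.* ITT difference = -0.10 x 334 / (334 + k).
- k = 5: -33.4 / 339 = -0.0985, shift 0.0015
- k = 25: -33.4 / 359 = -0.0930, shift 0.0070
- k = 38: -33.4 / 372 = -0.0898, shift 0.0102

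*As the SAP codes it.* A subject with no DCNVA data first gets a Visit 3 value drawn from the own arm, under either rule. The control regression then gives an expected Visit 4 value of r x (-0.10). Here r is the Visit 3 to Visit 4 correlation, assumed to be 0.3 to 0.7, with equal SDs and the same -0.10 difference at Visit 3. ITT difference = (-33.4 - 0.10 x r x k) / (334 + k).
- k = 25, r = 0.3: (-33.4 - 0.75) / 359 = -0.0951, shift 0.0049
- k = 25, r = 0.7: (-33.4 - 1.75) / 359 = -0.0979, shift 0.0021
- k = 38, r = 0.3 to 0.7: -0.0928 to -0.0969, shift 0.0072 to 0.0031

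**5. Against the decision threshold.** For k = 25, the smallest significant difference is 1.96 x 0.14 x sqrt(1/167 + 1/359) = 0.026. Every value above is far beyond it, and power stays above 99.99% even at k = 38.

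**6. DCIVA.** The same arithmetic applies if DCIVA has a scheduled visit before Visit 4. If Visit 4 is its first, the initial own-arm draw supplies the Visit 4 value itself, and for subjects with no data the shift is 0 as coded.

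**The case against.** The strongest reply is that this is mostly terminology. Much of it stands.

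- *A reader might infer that exclusions by arm are hidden, or that both checks are disabled.* The SAP does not support that. SAP 9 reports numbers not implanted and discontinuation reasons by arm. It also lists exit reason, eligibility criteria not met, and randomised and actual treatment by subject. Protocol 9.4.3 promises an investigation if ITT results differ materially. What can be lost is the distinction between reasons. The criteria-not-met listing recovers it only for ineligibility.
- *A reader might infer that every non-implanted subject is coded this way.* Protocol 5.3 has subjects with intraoperative events discontinued, and 8.2 has those not exposed exited. Neither attaches the label to them. Only the general wording of 5.4 or 7.1 could reach them.
- *The misrouting is conditional.* It depends on an Exit CRF that is not in the documents. Protocol 7.1 also lists investigator's request as a reason, and SAP 19 says the physician-decision term was matched to the eCRF. A site could record the true reason. But 7.1 gives no rule for choosing between the two codes, and its explicit instruction points to screen failure.
- *The sample code may make the label irrelevant.* The control-based step reads the dataset mcmc although the preceding step builds mcmc2. Run literally, it would impute all remaining monotone missing DCNVA data from control. The code is only illustrative, however, and the text of SAP 8.2 states the intended rule.
- *Control-based imputation of every investigator-initiated non-implantation is a debatable estimand choice.* Agreed. The point asks only that the SAP's own rule reach the subjects it names.

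**Conclusion.** The protocol uses one term in two incompatible ways, and the wider use miscodes randomised subjects. If the Exit CRF follows 7.1, the by-arm reasons table is less informative than it should be, and the ITT check for DCNVA and DCIVA leans slightly toward the test lens. The lean is about 0.002 to 0.005 logMAR for 25 subjects and at most about 0.010 at the extreme bound, against a planned effect of 0.10. These sizes rest on assumed counts and an assumed correlation.

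A reader might infer a threat to the superiority claims. The figures do not support that: BCDVA, the All-Implanted primary analysis and power are unaffected, and the ITT conclusion would not change at the planned effect. The case for acting is traceability. A reason not recorded at exit may not be recoverable after database lock.

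**What to change.** 1. In Protocol 5.4, 7.1 and 8.2, restrict screen failure to exits before randomisation, in line with 9.2 and SAP 9.
2. For randomised subjects not implanted, record the actual reason on the Exit CRF: physician decision, subject request, change in eligibility or intraoperative event.
3. In SAP 9, tabulate those reasons by randomised arm.
4. In SAP 13.1.2, state that subjects whose true reason is physician decision follow the existing physician-decision rule. Do not extend that rule automatically to intraoperative complications.

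The cost is wording in three protocol sections, minor form work, a table row and one SAP sentence. No endpoint, sample size or primary analysis changes. ITT estimates for near and intermediate acuity may become marginally less favourable to the test lens.
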